**11.2.8. Activities of Daily Living**

The change in ADL from Baseline at Weeks 24, 36, and 48 will be analyzed.

**11.2.9. Frequency of Falls**

The frequency of falls from Screening through Week 48 will be analyzed.

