**Investigational product, dosage and mode of administration:**

RTA 408 Capsules (2.5 mg, 10 mg, or 50 mg) will be administered orally.

Duration of treatment:
 
Part 1: RTA 408 or placebo administered orally once daily for 12 weeks; Part 2: RTA 408 or placebo administered orally once daily for 48 weeks; Extension: RTA 408 administered orally once daily until the drug is available through commercial channels, or until patient withdrawal, whichever is sooner.

Reference therapy, dosage, and mode of administration:
 
Matching placebo capsules will be administered orally (Part 1 and Part 2 only).

Criteria for evaluation:
 
Efficacy (Part 1): Parameters collected during maximal exercise testing (including peak work), FARS test (including mFARS score), 25-foot walk timed test, low-contrast letter visual acuity test, 9-HPT, Fatigue Severity Scale, SF-36, [REDACTED]
 
Efficacy (Part 2): FARS test (including mFARS score); parameters collected during maximal exercise testing (including peak work), 9-HPT, 25-foot timed walk test, ADL, SF-36, Patient Global Impression of Change, Clinical Global Impression of Change, and fall diary
 
Safety (Part 1 and Part 2): Results of echocardiogram, electrocardiogram (ECG), vital sign measurements, weight, body mass index (BMI), physical examinations, adverse events (AEs), serious adverse events (SAEs), concomitant medications, and laboratory test results (clinical chemistry, hematology, urinalysis, microscopy, and pregnancy tests [as indicated])
 
Safety (Extension): Vital sign measurements, physical examination results, AEs, SAEs, weight, and assessment of BNP and N-terminal prohormone of B-type natriuretic protein (NT-Pro BNP).
 
Pharmacokinetic (Part 1 and Part 2): RTA 408 plasma concentration data
 
Pharmacodynamic (Part 1): Parameters assessed from [REDACTED], platelet, [REDACTED] samples.
 
Extension: Results of physical examinations, laboratory results, vital sign measurements, weight, AEs, SAEs, concomitant medications, pregnancy tests [as indicated], FARS, ADL, 9-HPT, 25-foot timed walk test.

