### **6.2.3. Exploratory Objectives**

- To evaluate the distribution of change in mFARS scores at Week 48
- To evaluate the change in SF-36 score
- To evaluate the change in performance on a 9-HPT
- To evaluate the change in performance on a 25-foot timed walk test
- To evaluate the change in the Activities of Daily Living (ADL) score
- To evaluate the frequency of falls
- To characterize the PK of RTA 408 and potential metabolites after oral administration of RTA 408 Capsules

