Beginning with the second 8-patient cohort, once the eighth patient enrolled completes their Week 2 visit, the DSMB will review all available safety information and recommend the dose of RTA 408 for the subsequent cohort. The DSMB dose recommendation for each cohort must not exceed 100% more than the highest dose of RTA 408 previously evaluated in this study, and the maximum permitted dose of RTA 408 is 300 mg. The dose level for each new cohort will not exceed the DSMB recommended dose level, and it will be selected by the Sponsor based on review of available safety, efficacy, PK, and PD data. Prior to opening each cohort in Part 1 for enrollment, the Sponsor will evaluate all available data from doses studied in Part 1 to determine if enough information is available to select doses for Part 2 of the study. Once enrollment begins in Part 2, no additional cohorts will be enrolled in Part 1.

Part 2: The second part of this study will be a randomized, placebo-controlled, double-blind, parallel-group study to evaluate the safety and efficacy of RTA 408 150 mg in patients with Friedreich's ataxia. Patients enrolled in Part 2 will be randomized 1:1 to receive RTA 408 150 mg, or placebo. Randomization will be stratified by pes cavus status (pes cavus vs. no pes cavus). Patients with pes cavus, a musculoskeletal foot deformity characterized by high arch of the foot that does not flatten with weight-bearing, will comprise no more than 20% of patients enrolled in Part 2. The RTA 408 dose of 150 mg was selected for Part 2 based on DSMB and Sponsor review of available data from Part 1, including safety, efficacy, PK, and PD data. Following randomization on Day 1, patients will self-administer study treatment once daily for 48 weeks. A follow-up visit for safety will occur at Week 52 (4 weeks after last dose). The DSMB will perform quarterly reviews of unblinded data for safety throughout Part 2.

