h Blood samples should be collected for hepatitis B and C and HIV antibodies only in patients lacking evidence of a negative titer in the past year.

i Negative serum pregnancy test results are required at the Screening Visit before study enrollment, and negative urine pregnancy test results are required at all other times indicated for continued participation in the study.

j A dosing diary check must be performed at study drug return and pill count.

- k Study drug should be administered in the presence of study staff in the clinic on Day 1 after all Day 1 assessments have been completed. Study drug should also be administered in the clinic on Day 14 (Visit 4), Day 84 (Visit 7), Day 168 (Visit 9), and Day 336 (Visit 13) after the blood collection for predose PK analysis. All other doses can be administered at home. Study drug should be administered once daily through Day 336 (Visit 13).
- l On study days where multiple assessments are to be completed, the maximal exercise test will be the first functional assessment performed.
- m The practice FARS assessment is not required for patients having completed a FARS assessment within 90 days prior to Screening. The practice FARS assessment must be performed prior to the screening maximal exercise test.
- n Other than the practice FARS, all FARS assessments must always be performed after the maximal exercise test.
- o Both Screening and Day 1 mFARS are required to determine patient eligibility.
- p Video of the 25-foot timed walk test is optional and will be collected only for those patients who provide consent to video.
- q Patients who consent to video collection of the 25-foot timed walk test will also have video collection during normal walking with a 25-foot (un-timed) walk using his/her normal gait. The normal walk must be performed after the 25-foot timed walk test.
- r Patients and investigators must complete the patient global impression of change and clinical global impression of change following completion of the neurological FARS exam.
- s Patients will be provided the fall diary at Screening and must record fall incidents between Screening and Week 48.
- t Blood samples for PK analysis at Day 14 (Visit 4) should be collected prior to study drug administration as well as 1, 2, 4, and 8 hours after study drug administration.

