**8.5.2. Patient Termination Criteria**

Termination refers to a patient stopping study drug and all study assessments and visits. Reasons for study termination include the following:

- Administrative reasons (e.g., inability to continue, lost to follow-up)
- Death
- Withdrawal of consent

Patients who terminate the study for any reason may not re-initiate study drug or study assessments at any time.

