#### 14.2.3. Efficacy Variables

Part 1: Efficacy variables are peak work during maximal exercise testing, oxygen utilization during maximal exercise testing, mFARS scores, FARS score, 25-foot timed walk test distance,

9-HPT scores, low-contrast letter visual acuity test scores, Fatigue Severity Scale scores, and SF-36 scores.

Part 2: Efficacy variables are mFARS scores, full FARS scores, peak work during maximal exercise testing, parameters collected during maximal exercise testing (other than peak work), 9-HPT scores, 25-foot timed walk test distance, ADL, Patient Global Impression of Change, Clinical Global Impression of Change, and SF-36 scores.

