### **14.3. Statistical Analyses**

Separate SAPs will be written for each study part. The SAPs will detail the analyses to be performed for each study part and will be developed prior to the database lock of each study part. The SAPs, which will describe in detail the methods used for the primary and secondary endpoints, will serve as the final arbiter of all statistical analyses.

Data will be summarized using descriptive statistics. Continuous data will be summarized with number of patients (n), mean, median, minimum, maximum, standard deviation, coefficient of variation, and geometric mean (where applicable). Categorical data will be summarized using frequency counts and percentages.

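### Section 11.2.9 defines the exploratory falls endpoint from Screening, so read literally it includes up to 60 pre-dose days that would pull a rate ratio toward 1

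*Protocol*

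**What the plan says.** Falls are a Part 2 exploratory objective: "To evaluate the frequency of falls" (Protocol 6.2.3). The whole analysis statement, in 11.2.9, is "The frequency of falls from Screening through Week 48 will be analyzed". Diary collection is set separately, over the same span, in 9.9.35 and in Table 4 footnote s: "Patients will be provided the fall diary at Screening and must record fall incidents between Screening and Week 48".

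The Part 2 schedule (Table 4) places screening at Day -60 to Day -1 and Week 48 at Day 336, with a window of 3 days either side. Treatment starts only after allocation: "Following randomization on Day 1, patients will self-administer study treatment once daily for 48 weeks" (7.1).

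No supplied text says whether falls before Day 1 are a baseline, a covariate, excluded, or pooled with later falls. None defines the frequency measure or a model for it. Section 14.3 says of the SAPs that they "will serve as the final arbiter of all statistical analyses". The only SAP text supplied is a memo on what to do when sites are too sparse to serve as a covariate, and it does not mention falls.

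The variable lists also disagree. The Synopsis, under criteria for evaluation, ends its Part 2 efficacy list with "Patient Global Impression of Change, Clinical Global Impression of Change, and fall diary". The Part 2 list in 14.2.3 ends with "ADL, Patient Global Impression of Change, Clinical Global Impression of Change, and SF-36 scores" and does not include falls.

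**The concern.** Section 11.2.9 gives a span for analysis, not only for data collection, and that span begins before anyone is randomised. Falls between Screening and Day 1 cannot be affected by treatment, and randomisation makes their expected rate equal in the two arms. Pooling them with on-treatment falls adds the same expected number of falls and the same expected number of days to each arm, which moves a ratio of rates toward 1. The number of such days depends on how long each patient spent in screening, which has nothing to do with the treatment comparison.

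The neighbouring sections 11.2.5 to 11.2.8 are each worded as a change from Baseline. Section 11.2.9 is not, so its wording does not separate the pre-dose period from the rest. At stake is the size and precision of one exploratory estimate.

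**Working it through.** The documents state no fall rate, effect size or power for falls, so there is no planned figure to reproduce. The check is a day count followed by a dilution formula.

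**Inputs.** Screening days s: at most 60 (Table 4; Day -1 is the day before first dose). Post-dose days T: 336 (Week 48, Table 4). True rate ratio RR: not given, so 0.70 is assumed and other values are shown. Further assumptions are constant fall rates, equal rates in both arms before dosing, and a treatment effect from Day 1.

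**Pre-dose share** = s / (s + T)

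- s = 14: 14/350 = 4.0%
- s = 28: 28/364 = 7.7%
- s = 60: 60/396 = 15.2% (15.0% to 15.3% across the 3-day window at Week 48)

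**Ratio seen over Screening to Week 48** = (s + RR × T) / (s + T). With RR = 0.70, RR × T = 235.2.

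- s = 14: 249.2/350 = 0.712
- s = 28: 263.2/364 = 0.723
- s = 60: 295.2/396 = 0.745

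**Loss on the log scale** = 1 - ln(ratio seen)/ln(0.70): 4.8%, 9.1% and 17.6% respectively.

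**Other assumed ratios**, at s = 14 and s = 60:

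- 0.50 appears as 0.520 and 0.576
- 0.60 appears as 0.616 and 0.661
- 0.80 appears as 0.808 and 0.830
- 0.90 appears as 0.904 and 0.915

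**Shorter follow-up.** The diary can stop early: "Termination refers to a patient stopping study drug and all study assessments and visits" (8.5.2). For a patient with 60 screening days whose diary ends at Day 168, the pre-dose share is 60/228 = 26.3%. At that length of follow-up the formula gives (60 + 117.6)/228 = 0.779. This illustrates one pattern of follow-up and is not an estimate for the trial.

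**No effect.** With RR = 1 the formula gives (s + T)/(s + T) = 1. The null value is unchanged, so the choice of window does not in itself alter Type I error.

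**Difference in total counts.** With a placebo fall rate of λ per day, the expected totals are λ(s + T) and λ(s + RR × T). Their difference is λT(1 - RR), in which s cancels. The expected difference therefore does not move, but the pre-dose falls add variance. How much depends on fall rates and between-patient variation that the documents do not give.

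**The case against.** The strongest reply is that the rule may already exist. Section 14.3 makes the SAPs the final word, the memo confirms that a Part 2 SAP with specified programs existed, and the next section, 11.2.10, defers its cutoffs to the SAP. One-line protocol entries completed elsewhere are this document's habit. This stands: the gap is shown for the protocol and the memo only. It is tempered by 14.3 itself, which promises detailed methods specifically for primary and secondary endpoints, whereas falls are exploratory.

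Second, the sentence may simply name the data span, with screening falls meant as a baseline. A diary issued at Screening is what a baseline rate would need, and the objectives compare patients receiving RTA 408 with patients receiving placebo, which nobody receives before Day 1. This reading is open, and under it there is no dilution. The text does not choose between the two readings, and they give different estimates from the same diary.

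Third, 60 days is a ceiling. The documents give no actual screening durations, and short screening makes the effect small. Patients who only stop study drug are asked to complete all visits if possible (8.5.1), so early diary ends should come mainly from full termination. Both points stand.

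A reader might infer that the trial will understate any effect on falls by 15% or more. The documents do not support that. They name no rate ratio, and the figure would need every patient to be screened for the full 60 days and the falls to be pooled.

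**Conclusion.** The point holds as a minor one. Taken at its word, Section 11.2.9 sets a window that is worse than Day 1 to Week 48 for estimating a treatment effect. The pre-dose share is 4.0% with 14 screening days and at most 15.2% with 60, given follow-up to Day 336. A true rate ratio of 0.70 would then appear as 0.712 to 0.745.

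Those ratios rest on a rate ratio being the measure, constant rates, equal pre-dose rates by randomisation, and an assumed true effect. If a difference in counts is used, the cost is precision and not bias. No loss of power can be stated, because the documents give no fall rate, dispersion, effect or test. It would also be wrong to infer a threat to Type I error or to the primary or secondary endpoints, since neither depends on this window.

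Whether the main Part 2 SAP resolves the point is unknown from what was supplied. The absence of falls from 14.2.3 is a separate, editorial inconsistency that stands under either reading.

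**What to change.** First check the main Part 2 SAP. If it already sets a post-dose window, align 11.2.9 with it. Otherwise keep diary collection from Screening and replace 11.2.9 with wording such as:

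'The frequency of falls from first dose (Day 1) through Week 48, or the last diary day if earlier, will be analyzed as a rate with days observed as offset, adjusted for the Screening-to-Day 1 fall rate and pes cavus status; falls before Day 1 are baseline and are not counted in the endpoint.'

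Pes cavus status is the Part 2 stratification factor (7.1 and 9.4), so adjusting for it follows the design. Add falls to the Part 2 list in 14.2.3 so that it agrees with the Synopsis.

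No new data are needed, because the diary already covers both periods. Appendix 13 records that Part 2 was already complete at the time of the pandemic, so timing matters. If the change is made after unblinding, label the Day 1 to Week 48 result post hoc and show it beside the Screening to Week 48 result.

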**11.2.10. Distribution of Change in mFARS Scores**

The proportion of patients at Week 48 with an mFARS change from baseline at or lower than specified cutoff values defined in the SAP (e.g., -2, -3, etc.) will be analyzed.

## **12. SAFETY ASSESSMENTS**

### **12.1. Safety Parameters**

Safety parameters in Part 1 and Part 2 include results of echocardiogram, ECG, vital sign measurements, weight, BMI, physical examination, AEs, SAEs, concomitant medications, and laboratory tests (clinical chemistry, hematology, urinalysis, microscopy, assessment of BNP and NT-proBNP, and pregnancy tests [as indicated]). Safety parameters in the extension study include vital sign measurements, physical examination results, AEs, SAEs, weight, and laboratory tests (clinical chemistry, hematology, urinalysis, microscopy, assessment of BNP and NT-proBNP, and pregnancy tests [as indicated]).

### **12.2. Adverse and Serious Adverse Events**

#### **12.2.1. Definition of Adverse Events**

##### **12.2.1.1. Adverse Event**

An AE is defined as any untoward medical occurrence in a patient regardless of its causal relationship to study treatment. An AE can be any unfavorable and unintended sign (including any clinically significant abnormal laboratory test result), symptom, or disease temporally associated with the use of the study drug, whether or not it is considered to be study drug related. Included in this definition is any newly occurring event or previous condition that has increased in severity or frequency since the administration of study drug.

Pre-planned elective procedures (surgeries or therapies) that are performed to manage/treat conditions that existed prior to the patient's enrolling in the trial (e.g., elective periodontal surgery, elective hernia repair) should not be recorded as AEs, but should be documented in the patient's source documents. If a pre-planned procedure is performed early (e.g., as an emergency) because the pre-existing condition worsens, the worsening condition should be captured as an AE.

All AEs that are observed or reported by the patient during the study (from the time of the first dose of study drug until the final visit or 30 days following final study dose for patients who terminate early) must be reported, regardless of their relationship to study drug or their clinical significance.

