Maximal exercise test d	X	X			X		X	X	X		X		X	
Neurologic FARS (practice)	X m													
Neurologic FARS n	X o	X o			X		X	X	X		X		X	
9-hole peg test	X	X							X				X	
25-foot timed walk test	X	X p							X p				X p	
Video Collection of Normal Walking q		X							X				X	
SF-36 Health Survey Update		X							X				X	
Activities of Daily Living	X								X		X		X	
Patient Global Impression of Change							X r		X r		X r		X r	
Clinical Global Impression of Change							X r		X r		X r		X r	
Falls Diary	X s		←-----X-----→											
PK analysis				X t			X u		X u				X u	

Abbreviations: BMI=body mass index; BNP= B-type natriuretic peptide; FARS=Friedreich’s ataxia rating scale; HIV=human immunodeficiency virus; NT-proBNP=N-terminal prohormone of B-type natriuretic peptide; PK=pharmacokinetic; WOCBP=women of childbearing potential.

a These procedures should also be performed in the event of early termination.

b Study Day -1 is the day prior to first dose of study drug.

c All Day 1 procedures should be performed prior to administration of first dose of study drug.

d Only 1 x-ray will be collected during the study. Only x-rays of the right foot will be completed for the foot x-ray assessment. Patients should complete the x-ray foot assessment at Screening; however, if the patient was not able to complete the x-ray foot assessment at Screening, it may be completed during any visit while the patient is participating in the study.

e For patients with echocardiograms and electrocardiograms collected within 90 days prior to the Screening Visit, the most recent echocardiogram and electrocardiogram can be used to assess patient eligibility.

f A home health nurse visit may be used to collect all lab samples required at the Screening Visit.

g Patients must be allowed to rest for a minimum period of 1 hour following maximal exercise test before this blood sample is collected (at the same time as all central lab blood draws). This sample should be taken with the patient in the same position (e.g., sitting or semi-recumbent) at all appropriate visits.

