#### **9.9.13. Physical Examination**

A comprehensive physical examination must be performed by a physician, physician assistant, or registered nurse practitioner at the times indicated in [Table 3](#), [Table 4](#), and [Table 5](#). If possible, the same individual should perform each physical examination on a patient during the study. The examination must include the following organ or body system assessments: general appearance, head, eyes, ears, nose, throat, neck, musculoskeletal, cardiovascular, lymphatic, respiratory, abdomen, dermatologic, extremities, and neurological. Assessments of any specific signs or symptoms reported by the patient must also be performed and documented along with any other findings of note. Each body system finding must be assessed for clinical significance. Clinically significant findings at the Screening Visit must be included in the patient's medical history. New clinically significant findings after first dose must be included as AEs. Subsequent assessments beyond screening should be characterized as new, worsening, improved, or unchanged relative to the previous assessment.

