#### **9.9.26. Maximal Exercise Test**

Cycle ergometry using a recumbent stationary bicycle will be used to conduct maximal exercise testing at the times indicated in Table 3 and Table 4. An example of the procedures for maximal exercise testing is provided in Appendix 2. Procedures for maximal exercise testing will be included in a study manual. Maximal exercise testing assessments include but are not limited to peak work and peak oxygen utilization. On study days where multiple assessments are to be completed, the maximal exercise test must be the first functional assessment performed.

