##### **12.2.1.2. Serious Adverse Event**

An SAE is any AE occurring at any dose and regardless of causality that:

- Results in death
- Is life-threatening
- Requires inpatient hospitalization or prolongation of existing hospitalization
- Results in persistent or significant incapacity or substantial disruption of the ability to conduct normal life functions
- Is a congenital anomaly or birth defect in an offspring of a patient taking study drug

- Is an important medical event

The term "life-threatening" refers to an event in which the patient was at immediate risk of death at the time of the event. It does not refer to an event that hypothetically might have caused death if it were more severe.

Important medical events are those that may not meet any of the criteria defined above; however, they may be considered serious when, based upon appropriate medical judgment, they may jeopardize the patient and may require medical or surgical intervention to prevent one of the other outcomes listed in the SAE definition.

Pregnancy is not considered an AE; however, information will be collected for any pregnancies that occur during the study (from the time of first dose of study drug until the final visit). Certain pregnancy outcomes will require submission as an SAE (Section 9.7.3).

The investigator is responsible for reporting to the Sponsor or its designee all AEs and SAEs that are observed or reported by the patient during the study (from the time of first dose of study drug until the final visit), regardless of their relationship to study drug or their clinical significance. All SAEs reported or observed during the study must be followed to resolution or until the investigator deems the event to be chronic or the patient to be stable. The Sponsor or its designee may contact the investigator to obtain additional information on any SAE that has not resolved at the time the patient completes the study.

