## 12.6. Recording Adverse Events

All conditions present prior to the first dose of study drug should be documented as medical history. All drug-related (characterized as possibly or probably related; Section 12.4) AEs and abnormal laboratory test results reported or observed during the study must be followed to resolution (either return to baseline or within normal limits). All other AEs or non-drug-related abnormal laboratory results will be followed through the final visit (i.e., end of study or early termination). Information to be collected includes type of event, date of onset, date of resolution, investigator-specified assessment of severity and relationship to study drug, seriousness, as well as any action taken.

While an AE is ongoing, changes in the severity (e.g., worsening or improving) should be noted in the source documents but when documenting the AE, only the total duration and greatest severity should be recorded in the CRF. AEs characterized as intermittent require documentation of onset and duration.

AEs resulting from concurrent illnesses, reactions to concurrent illnesses, reactions to concurrent medications, or progression of disease states must also be reported. Pre-existing conditions (present before the start of the AE collection period) are considered concurrent medical conditions and should NOT be recorded as AEs. However, if the patient experiences a worsening or complication of such a concurrent condition, the worsening or complication (except disease progression) should be recorded as an AE. Investigators should ensure that the AE term recorded captures the change in the condition (e.g., "worsening of...").

Each AE should be recorded to represent a single diagnosis. Accompanying signs (including abnormal laboratory test values or ECG findings) or symptoms should NOT be recorded as additional AEs. If a diagnosis is unknown, sign(s) or symptom(s) should be recorded as an AE(s). Changes in laboratory test values or ECG parameters are only considered to be AEs if they are judged to be clinically significant (i.e., if some action or intervention is required or if the

investigator judges the change to be beyond the range of normal physiological fluctuation). If abnormal laboratory test values or ECG findings are the result of pathology for which there is an overall diagnosis (e.g., increased creatinine levels in renal failure), only the diagnosis should be reported as an AE.

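### AE and SAE reporting opens at first dose, so events at the required Screening maximal exercise test need not be reported to the sponsor, and for the Day 1 test the protocol contradicts itself

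*Protocol*

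**What the plan says.** **Reporting window.** Section 12.2.1.1 requires AEs to be reported "from the time of the first dose of study drug until the final visit or 30 days following final study dose"; the 30-day limit is for patients who terminate early. Section 12.2.1.2 gives the investigator's duty to report AEs and SAEs to the sponsor the same start: "from the time of first dose of study drug until the final visit". SAEs have no earlier window of their own.

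**Events before dosing.** Section 12.6 states: "All conditions present prior to the first dose of study drug should be documented as medical history". Section 9.9.13 draws the same line for examinations: "New clinically significant findings after first dose must be included as AEs".

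**Exercise tests before dosing.** Section 9.9.26 has sites "conduct maximal exercise testing at the times indicated in Table 3 and Table 4". Both tables mark the test at Screening and on Day 1. Table 4 footnote m confirms the first of these for Part 2: "The practice FARS assessment must be performed prior to the screening maximal exercise test". Footnote c of Table 4, repeated in Table 3, adds: "All Day 1 procedures should be performed prior to administration of first dose of study drug". Section 17.3 places consent before any study-specific procedure, so these are consented participants.

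**AE row of the schedules.** Tables 3 and 4 have no AE mark at Screening, but do have one on Day 1.

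**The concern.** The maximal exercise test is the most strenuous procedure in the protocol. Patients with mild to moderate cardiomyopathy related to Friedreich's ataxia may enrol. A reporting window tied to first dose suits treatment-emergent tables, but it leaves out harm caused by what the trial itself requires before dosing.

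What is at stake is oversight. Under Section 7.5 the DSMB assesses AEs and reviews SAEs from the safety database. A serious event at a Screening test is not required to enter that database. In a randomised patient it could be recorded only as medical history. In a patient who then fails screening, no first dose is given and the window never opens. The uncovered period lasts up to 28 days in Part 1 (Table 3) and up to 60 days in Part 2 (Table 4).

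**Working it through.** The plan gives no figure to reproduce. The check is a reading of the text followed by a count.

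**Step 1: does another section close the gap at Screening?**
- Section 12.3 requires patients to be asked at every visit about hospitalisation and accidents, but says only that the answers go into source documents.
- Section 12.7 sets a 24-hour rule for serious AEs. It relies on the AE definition already given and sets no earlier start.
- Section 12.4 classifies relation to study drug only; there is no category for relation to a study procedure.
- Section 17.5 gives a general duty to tell the IRB about problems involving risk. That is not sponsor or DSMB reporting.
- Section 18.2 describes electronic data capture for all consented patients, but does not extend AE reporting to the pre-dose period.

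None of these requires a pre-dose event to be reported to the sponsor as an AE or SAE. The supplied SAP document covers only the replacement of site as a covariate and does not bear on this.

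**Step 2: is Day 1 covered?** Tables 3 and 4 mark AE collection on Day 1, and their footnote c places Day 1 procedures before the first dose. Read together, AE collection that day comes before dosing. Section 12.2.1.1 says the window has not yet opened. The extension schedule (Table 5, footnote c) puts its Day 1 AE assessment after dosing, but Tables 3 and 4 carry no such note. The documents do not settle the matter, so both readings are counted below.

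**Step 3: count.** Inputs:
- Part 1 tests per patient (Table 3): Screening, Day 1, Week 4, Week 12 = 4.
- Part 2 tests per patient (Table 4): Screening, Day 1, Weeks 4, 12, 18, 24, 36, 48 = 8.
- Planned enrolment (Section 7.2): up to 72 in Part 1, about 100 in Part 2.

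Uncovered share = uncovered tests per patient ÷ scheduled tests per patient. Uncovered tests = uncovered tests per patient × patients. Scheduled total = 72 × 4 + 100 × 8 = 288 + 800 = 1,088.

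| | Screening only (Day 1 mark in the tables governs) | Screening and Day 1 (Section 12.2.1.1 governs) |
|---|---|---|
| Part 1 | 1/4 = 25%; 72 × 1 = 72 | 2/4 = 50%; 72 × 2 = 144 |
| Part 2 | 1/8 = 12.5%; 100 × 1 = 100 | 2/8 = 25%; 100 × 2 = 200 |
| Both | 172/1,088 = 15.8% | 344/1,088 = 31.6% |

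Tests in patients who fail screening come on top; the documents do not give their number. Section 8.4 allows one rescreening, including after failure of the mFARS agreement rule, which is judged on Day 1. In Part 2, footnote n of Table 4 puts the FARS after the exercise test, so such a patient could complete up to 2 + 2 = 4 tests before any dose.

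**The case against.** Three stronger readings are tempting, and the documents do not support them.

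*That pre-dose serious events go unreported altogether.* They may appear in source documents (Section 12.3), in medical history (Section 12.6) or in a report to the IRB (Section 17.5), and an investigator may report voluntarily. What is missing is the requirement to report them to the sponsor as AEs or SAEs.

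*That both pre-dose tests clearly lie outside the window.* The Day 1 mark in Tables 3 and 4 prevents that conclusion. Only the Screening test is clearly uncovered, so 200 tests in Part 2 is the upper figure for randomised patients, not a minimum.

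*That the DSMB cannot see harm from exercise testing.* Six of the eight Part 2 tests follow first dose, and Section 12.2.1.1 requires AEs from then on to be reported whatever their cause. Section 7.5 also gives the DSMB exercise-test data. Only pre-dose harm is in question.

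Two further objections carry weight. Eligibility limits cardiac risk: ejection fraction of at least 40%, BNP not above 200 pg/mL, and exclusion of clinically significant cardiac disease. The count of tests therefore says nothing about how many events to expect. Against that, the protocol does not say that these results must be available before the Screening test, and Table 4 footnote g has the BNP sample wait at least an hour after exercise. The study manual, which is not among the documents, may say more. Second, Appendix 13 states that Parts 1 and 2 were complete by the time of the pandemic, and Table 5 schedules no maximal exercise test in the extension. A change to the window would alter collection for no current patient. That limits the remedy but does not remove the gap.

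**Conclusion.** The point holds in limited form. By an explicit rule, events at the Screening maximal exercise test are not required to be reported to the sponsor as AEs or SAEs and need not reach the DSMB. This covers 1 of 8 tests per Part 2 patient (about 100) and 1 of 4 per Part 1 patient (up to 72), plus screen failures. For the Day 1 test the protocol contradicts itself. If Section 12.2.1.1 governs, the uncovered tests rise to 200 in Part 2 and 144 in Part 1.

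The counts assume planned enrolment and completion of every scheduled test. They measure uncovered procedures; the documents give no event rate from which to estimate harm. The gap concerns safety oversight and the completeness of the safety record. It changes no efficacy analysis and no treatment-emergent comparison.

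**What to change.** - **Sections 12.2.1.1 and 12.2.1.2:** collect and report all SAEs, and any AE related to a study procedure, from informed consent. Keep all other AEs from first dose.
- **Section 12.6:** amend so that these events are not filed only as medical history. Without this, the new window would contradict it.
- **Section 12.4:** add an item for relation to a study procedure.
- **Tables 3 and 4:** add Screening to the AE row, and reconcile the Day 1 AE mark with footnote c and with Section 12.2.1.1.
- **Reporting:** show pre-dose events in a separate listing that includes screen failures.

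Applied prospectively, this costs a few extra forms and one listing; treatment-emergent tables stay as they are. In the present version, with Parts 1 and 2 complete, it reduces to a retrospective listing of pre-dose events drawn from source documents and medical history. That listing may be incomplete. Medical history is scheduled only at Screening in Tables 3 and 4, so it need not have captured a Day 1 event, and anything never written down cannot be recovered. The study report should say so.
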